5.3 LIFESTYLE CONSIDERATIONS

5.3.1 Meals and dietary restrictions

Not applicable.

5.3.2 Caffeine, alcohol, and tobacco

Use of inhaled tobacco products (eg, smoking tobacco, vaping, heated tobacco, etc) and marijuana products will not be allowed from 6 months prior to Screening (Visit 1) until after the final follow-up visit. If abstinence is difficult for the participant, the participants may seek medical help and receive supportive treatment with Nicotine Replacement Therapy (NRT), by oral, or transdermal administration (but not inhalation or intranasal). Use of non-pharmaceutical products intranasally is prohibited.

5.3.3 Activity

Not applicable.

5.3.4 Other restrictions

Not applicable.

5.4 SCREEN FAILURES

A screen failure occurs when a participant who consents to participate in the clinical study is not subsequently randomized. A minimal set of screen failure information is required to ensure transparent reporting of screen failure participants to meet the CONSORT publishing requirements and to respond to queries from regulatory authorities. Minimal information includes demography, screen failure reasons, eligibility criteria, and any SAE.

If certain dynamic laboratory tests do not meet the inclusion criteria at Screening (Visit 1), these laboratory assessments may be repeated, at the discretion of the Investigator, if the parameter result is judged to be likely to return to acceptable range for study inclusion within the Screening period prior to Baseline (Visit 2). There is no need to screen fail such participants if the test finally meets the inclusion criteria.

Individuals who do not meet the criteria for participation in this study (screen failure) may be re-screened. Re-screened participants should be assigned a new participant number for every re-screening event. In this situation, the re-screened participant should sign a new ICF.

5.5 CRITERIA FOR TEMPORARILY DELAYING

During a regional or national emergency declared by a governmental agency, if the site is unable to adequately follow protocol-mandated procedures, contingency measures are proposed in Appendix 9: ([Section 10.9](#): Contingency measures for a regional or national emergency that is declared by a governmental agency) should be considered for screening/enrollment/randomization/administration of study intervention.

6 STUDY INTERVENTION(S) AND CONCOMITANT THERAPY

Study interventions are all pre-specified, IMPs and AxMPs, medical devices and other interventions (eg, surgical and behavioral) intended to be administered to the study participants during the study conduct.

6.1 STUDY INTERVENTION(S) ADMINISTERED

6.1.1 Investigational medicinal product(s)

The IMP is to be administered every 14 +/- 3 days (Q2W; itepekimab or placebo) (up to 26 doses) or 28 +/- 3 days (Q4W; itepekimab) (up to 13 doses) with placebo injection in between during the treatment period (Table 4). Each PFS contains a deliverable volume of 2 mL with an itepekimab concentration of 150 mg/mL or 0 mg/mL.

The IMP will be administered by the Investigator/designee, participants/caregivers (under the supervision of the Investigator/delegate or after sufficient training), or health care professional (in case of exceptional circumstances) following clinic procedures and blood collection (if applicable). Participants should be monitored for at least 30 minutes after administration of the first 3 IMP injections at the site by the site staff. The monitoring period may be extended as per country-specific or local site specific requirements.

The SC injection sites should alternate between the left or right upper thighs, 4 quadrants of the abdomen, or the left or right upper arms, so that the same site is not injected twice during consecutive visits.

To train participants or their caregivers how to prepare and inject IMP, the Investigator will first train the participant at an onsite visit during the treatment period. At this visit, the participant will perform the injection under the supervision of the Investigator or delegate. At subsequent study visits, participants will be trained to self-inject IMP or caregivers will be trained to inject IMP to the participant, and they are allowed to inject IMP at home after a minimum of 3 self-administered injections at investigational site from Visit 4 (Week 6) onwards. All trainings shall be documented in the participant's study file as well as the determination and clearance for the participant's and/or caregiver's to complete an injection at home. Prior to Visit 4 (Week 6) injections cannot be administered at home by a participant or caregiver, but in exceptional circumstances this will be allowed by a health care professional. The participant should only perform the injection in the abdomen, or left or right upper thighs. The caregiver can perform the injection in left or right upper thighs, the abdomen, or left or right upper arms. The site of administration during the previous site visit should be taken into consideration (the same site should not be injected twice during consecutive visits). The participant or caregiver should also be instructed to monitor for any reaction following injection per country-specific or local site specific requirements. The start date for home administration by participant or caregiver can be postponed temporarily or indefinitely if this is considered necessary by the Investigator or preferred by the participant or caregiver. In that case, the participant will be asked to return to the investigational site for their IMP injections or have IMP administered by a home nurse (if appropriate).

Table 4 - Investigational medicinal product(s) administered

Intervention label	SAR440340/RGN3500	SAR440340/RGN3500	Placebo
Intervention name	Itepekimab	Itepekimab	Placebo matching Itepekimab
Intervention description	SC injection, 300 mg Q2W	SC injection, 300 mg Q4W	SC injection, placebo Q2W
Type	Biological/Vaccine	Biological/Vaccine	Biological/Vaccine
Dose formulation	Prefilled syringe	Prefilled syringe	Prefilled syringe
Unit dose strength(s)	150 mg/mL	150 mg/mL	0 mg/mL
Dosage level(s)	300 mg Q2W	300 mg Q4W with alternating placebo administration at the 2-week interval between IMP.	0 mg/mL Q2W
Route of administration	SC injection	SC injection	SC injection
Use	Experimental	Experimental	Experimental
Packaging and labeling	Study intervention will be provided in PFS. Each PFS will be labelled as required per country requirement.	Study intervention will be provided in PFS. Each PFS will be labelled as required per country requirement.	Study intervention will be provided in PFS. Each PFS will be labelled as required per country requirement.
[Current/former name(s) or alias(es)]	Itepekimab	Itepekimab	Not applicable

Abbreviations: IMP = investigational medicinal product; PFS = prefilled syringe; Q2W = every 2 weeks; Q4W = every 4 weeks; SC = subcutaneous.

6.1.2 Auxiliary medicinal product(s)

Table 5 - Auxiliary medicinal product administered

Intervention label	MFNS
Intervention name	Mometasone furoate nasal spray; ATC code R01AD
Intervention description	MFNS 50 µg/actuation administered 2 actuations per nostril twice daily (400 µg total dose per day) or once daily for participants who cannot tolerate twice daily (200 µg total dose).
Type	Drug
Dose formulation	Solution for administration via spray pump.
Unit dose strength(s)	50 µg/actuation
Dosage level(s)	100 µg/nostril (2 actuations) bilaterally twice daily.
Route of administration	Intranasal spray
Use	Background treatment
Packaging and labeling	Varies and depends on pharmaceutical presentation and countries
Current/former name(s) or alias(es)	Mometasone furoate

Abbreviations: ATC = Anatomical Therapeutic Chemical; MFNS = mometasone furoate nasal spray.

6.1.3 Study arms

Table 6 - Study arm(s)

Arm title	300 mg Q2W	300 mg Q4W	Placebo
Arm type	Experimental	Experimental	Placebo
Arm description	Participants will receive itepekimab 300 mg Q2W as SC injection for up to 52 weeks.	Participants will receive itepekimab 300 mg Q4W with alternating placebo administration at the 2-week interval between active IMP as SC injection for up to 52 weeks.	Participants will receive placebo Q2W as SC injection for up to 52 weeks.
Associated intervention labels	NA	NA	NA

Abbreviations: IMP = investigational medicinal product; Q2W = every 2 weeks, Q4W = every 4 weeks, SC = subcutaneous.

The IMP and AxMP may be supplied at the site or in case of regional/national emergency from the Investigator/site/Sponsor to the participant via a Sponsor-approved courier company where allowed by local regulations and agreed upon by the participant.

For a regional or national emergency declared by a governmental agency that results in travel restrictions, confinement, or restricted site access, contingency measures are included in Appendix 9: ([Section 10.9](#): Contingency measures for a regional or national emergency that is declared by a governmental agency).

6.1.4 Devices

The itepekimab PFS is classified as a combination product with an integral medical device where the principal mechanism of action is that of the itepekimab (See [Section 8.4.9](#) Guidelines for Reporting Product Complaints for product complaints). Medical devices for diagnostic interventions (eg, ECG) are not considered as “investigational device” in the context of this study.

6.2 PREPARATION, HANDLING, STORAGE, AND ACCOUNTABILITY

1. The Investigator or designee must confirm appropriate conditions (eg, temperature) have been maintained during transit for all study intervention received and any discrepancies are reported and resolved before use of the study intervention.
2. Only participants enrolled in the study may receive study intervention and only authorized site staff (or participant/caregiver after formal training) may supply, prepare, or administer study intervention.
3. All study intervention must be stored in a secure, environmentally controlled, and monitored (manual or automated) area in accordance with the labeled storage conditions with access limited to the Investigator and authorized site staff.
4. The Investigator, institution, or the head of the medical institution (where applicable), or authorized site staff is responsible for study intervention accountability, reconciliation, and record maintenance (ie, receipt, reconciliation, and final disposition records).

Any quality issue noticed with the receipt or use of an IMP/AxMP (deficiency in condition, appearance, pertaining documentation, labeling, expiration date, etc) must be promptly notified to the Sponsor. Some deficiencies may be recorded through a complaint procedure (see [Section 8.4.9](#)).

A potential defect in the quality of IMP may be subject to initiation of a recall procedure by the Sponsor. In this case, the Investigator will be responsible for promptly addressing any request made by the Sponsor, in order to recall the IMP and eliminate potential hazards.

Under no circumstances will the Investigator supply IMP to a third party, allow the IMP to be used other than as directed by this clinical trial protocol, or dispose of IMP in any other manner.

6.3 ASSIGNMENT TO STUDY INTERVENTION

All participants will be centrally assigned to randomized study intervention using an IRT. Before the study is initiated, the telephone number and call-in direction for the Interactive Voice Response System (IVRS) and/or the log in information and direction for the Interactive Web Response System (IWRS) will be provided to each site.

Definition of a randomized participant is a participant from screened population who has been allocated to a randomized intervention regardless of whether the intervention was received or not. A participant cannot be randomized more than once in the study. The randomized intervention kit number list is generated centrally by Sanofi. The IMPs are packaged in accordance with this list. Study intervention will be dispensed at the study visits as summarized in the SoA ([Section 1.3](#)).

During the randomization process, participants will be stratified by asthma/AERD status (no asthma, asthma only, asthma & AERD), and region (Asia or rest of the world).

6.4 BLINDING

This is a double-blind study in which participants/care providers/Investigators/outcomes assessors are blinded to study intervention. The IRT will be programmed with blind-breaking instructions. In case of an emergency, the Investigator has the sole responsibility for determining if unblinding of a participant's intervention assignment is warranted (eg, in case of available antidote). Participant safety must always be the first consideration in making such a determination. If the Investigator decides that unblinding is warranted, he/she may, at the Investigator's discretion, contact the Sponsor to discuss the situation prior to unblinding a participant's intervention assignment unless this could delay emergency treatment for the participant. If a participant's intervention assignment is unblinded, the Sponsor must be notified within 24 hours of this occurrence. The date and reason for the unblinding must be recorded.

The bioanalyst and pharmacokineticist responsible for the sample analysis and PK evaluation will be unblinded. They will, however, agree not to disclose the randomization schedule or the individual unblinded analytical results before the database lock.

Sponsor safety staff may unblind the intervention assignment for any participant with an SAE for the purpose of expedited regulatory reporting (see [Section 8.4.4](#)). Sponsor staff involved in the conduct of the study will remain blinded to the participant intervention assignment.

Methods of blinding

Itepekimab and placebo will be provided in identically matched 2-mL PFS. To protect the blind, each treatment kit of 2-mL (itepekimab/placebo) glass PFS will be prepared such that the treatments (itepekimab and its matching placebo) are identical and indistinguishable and will be labeled with a treatment kit number.

In accordance with the double-blind design, study participants, Investigators, and study site personnel will remain blinded to study treatment and will not have access to the randomization scheme or to the IMP content (itepekimab or placebo) except under circumstances described above in this section.

6.5 STUDY INTERVENTION COMPLIANCE

When participants are dosed at the site, they will receive study intervention directly from the Investigator or designee, under medical supervision. The date and time of each dose administered in the clinic will be recorded in the source documents and recorded in the eCRF. The dose of study intervention and study participant identification will be confirmed at the time of dosing by a member of the study site staff other than the person administering the study intervention. During scheduled telephone contacts as per SoA, the site should verify the IMP compliance/ administrations with the participants and at next visit check the completion of the paper administration form(s).

When participants self-administer study intervention(s) at home, compliance with study intervention will be assessed at each subsequent phone or site visit. Compliance will be assessed by direct questioning, and counting returned empty labelled cartons during the site visits and documented in the source documents and relevant form. Deviations from the prescribed dosage regimen have to be recorded.

A record of the quantity of IMP dispensed to and administered by each participant must be maintained and reconciled with study intervention and compliance records. Intervention start and stop dates, including dates for intervention delays and/or dose reductions will also be recorded.

Compliance with AxMP will be checked and recorded at each visit by site staff.

6.6 DOSE MODIFICATION

Dose interruption of MFNS is permitted at the site Investigator's discretion to manage side effects. Participants may continue in the study if MFNS dosing is interrupted or permanently discontinued.

6.6.1 Retreatment criteria

Not applicable.

6.7 CONTINUED ACCESS TO INTERVENTION AFTER THE END OF THE STUDY

After the end of the study, a separate LTS18420 may be offered to participants who completed the study and are still taking the IMP. This LTS18420 will allow to assess long-term safety and efficacy of the itepekimab and will be described in a separate protocol.

If the LTS18420 is not conducted, and depending on the participant's unmet medical need, the non-availability of suitable alternative therapies, and an assessment of what is known about the benefits and risks of itepekimab, participants who have successfully completed their participation in this clinical trial (completed EOS Visit) will be eligible for post-trial access to itepekimab.

The Investigator/treating physician will determine if access to itepekimab is the best medical option for the participant and will then submit a request to the Sponsor, if allowed by local regulations.

Provision of itepekimab will be in compliance with all applicable national and local laws and regulations, including safety reporting obligations.

A participant will not be eligible for post-trial provision of itepekimab if his/her participation in the trial is terminated prematurely.

The Sponsor's post-trial access responsibilities will need to be periodically re-evaluated. Based on new information about the IMP (including adverse reactions), the continued health benefit to the individual and market availability of the product or alternative therapies, post-trial access may be terminated. This includes situations where the trial may be stopped due to safety concerns or other issues.

6.8 TREATMENT OF OVERDOSE

Symptomatic overdose is an AESI (defined in [Section 8.4.7](#)). No antidote is available for itepekimab.

An overdose (accidental or intentional) with the IMP is an event suspected by the Investigator or spontaneously notified by the participant and defined as at least twice the intended dose during an interval of <8 days.

In the event of an overdose (symptomatic or asymptomatic), the Investigator/treating physician should:

1. Contact the Sponsor or Sponsor representative(s) immediately.
2. Closely monitor the participant for any AE/SAE and laboratory abnormalities.

3. Obtain a serum sample for PK analysis as soon as possible from the date of the last dose of study intervention if requested by the Sponsor or Sponsor representative(s) (determined on a case-by-case basis).
4. Document appropriately in the eCRF.

Decisions regarding dose interruptions or modifications will be made by the Investigator in consultation with the Sponsor or Sponsor representative(s) based on the clinical evaluation of the participant.

6.9 PRIOR AND CONCOMITANT THERAPY

Any medication or vaccine (including over-the-counter or prescription medicines, recreational drugs, vitamins, and/or herbal supplements) that the participant is receiving at the time of enrollment or receives during the study must be recorded along with:

- Reason for use.
- Dates of administration including start and end dates.
- Dosage information including dose route and frequency.

The Sponsor should be contacted if there are any questions regarding concomitant or prior therapy.

The following concomitant treatments are not permitted during the screening period and the randomized treatment period:

- Anti-IL5 or IL5R mAb (eg, benralizumab, mepolizumab, reslizumab, depemokimab).
- Anti-TSLP (tezepelumab).
- Anti-IgE therapy (eg, omalizumab).
- Anti-IL4 receptor mAb (eg, dupilumab).
- Other mAbs including anti-IL6, anti-IL17, anti-IL23, anti-IL12/23, anti-IL13, etc.
- Systemic immunosuppressants (eg, methotrexate, any anti-TNF mAbs, B and/or T-cell targeted immunosuppressive therapies, JAK inhibitors).
- Other investigational drugs.
- Live-attenuated vaccines (Appendix 15 [Section 10.15](#)).
- Allergen immunotherapy (except if initiated more than 3 months prior to Visit 1 and dose stable 1 month prior to Visit 1).
- INCS drops or sprays other than MFNS (except in Japan and China).
- Long-term courses (>2 weeks) of SCS.
- Initiation of maintenance antibiotic therapy is prohibited.
- Xhance, device.

- Intranasal emitting devices/ stents.
- Initiation of leukotriene antagonists/modifiers unless on stable dose for ≥ 30 days prior to Screening (Visit 1).
- Oral or intranasal decongestants other than single use during endoscopy as below.

Participants who between Visit 1 and Visit 2 receive any of the prohibited treatments, or treatment with SCS (oral, IV, IM, SC) or undergo surgery will not be randomized. They may however be re-screened following the procedures described in [Section 10.1](#).

The following is a list of concomitant medications that are permitted during the study:

- Nasal normal saline.
- Single intranasal decongestants administration eg, oxymetazoline hydrochloride (to reduce the swelling and widen the path for the endoscope), as well as a topical anesthetic, eg, lidocaine are allowed before endoscopy.
- Short-acting beta-agonist (SABA), LABA, and LAMA.
- Methylxanthines (eg, theophylline, aminophyllines).
- Inhaled CSs.
- Systemic antihistamines.
- Rescue medication including short courses of SCS for treatment of NP as described in [Section 6.9.1](#) of the Protocol or short courses of SCS to treat other serious co-existing diseases (such as asthma exacerbation) are allowed.

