This study consists of three periods with a study duration of approximately 76 weeks for all participants:

- Screening run in on MFNS for 4 weeks.
- Randomized itepekimab/placebo intervention period (52 weeks).
- Post-IMP treatment safety follow-up (20 weeks).

Eligible participants who complete the treatment period will be offered the opportunity to participate in an open-label LTS18420 study with itepekimab if approved by Health Authority & Ethical Committees.

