- E 08. History of malignancy within 5 years before Screening (Visit 1), or during the screening period, except completely treated in situ carcinoma of the cervix, completely treated and resolved nonmetastatic squamous or basal cell carcinoma of the skin, and precancerous lesions or disorders.
- E 09. Participants with a history of a severe systemic hypersensitivity reaction to a mAb.

- E 10. Participants with conditions/concomitant diseases making them non-evaluable at Visit 1 or for the primary efficacy endpoint such as:
- Antrochoanal polyps.
 - Nasal septal deviation that would occlude at least one nostril.
 - Acute sinusitis, nasal infection, or upper respiratory infection.
 - Ongoing rhinitis medicamentosa.
 - Allergic granulomatous angiitis (Churg-Strauss syndrome), granulomatosis with polyangiitis (Wegener's granulomatosis), Young's syndrome, Kartagener's syndrome or other dyskinetic ciliary syndromes, concomitant cystic fibrosis.
 - Radiologic suspicion or confirmed invasive or expansive fungal rhinosinusitis.
- E 11. Participants with nasal cavity malignant tumor and benign tumors (eg, papilloma, blood boil etc).
- E 12. Participants with severe uncontrolled asthma with history of 2 and/or more exacerbations, requiring SCS or 1 hospitalization requiring SCS in the past year.
- E 13. History of concomitant lung disease (other than asthma, eg, COPD, interstitial lung disease) which in the opinion of the Investigator could interfere with performance and interpretation of spirometry.

Prior/concomitant therapy

- E 14. Initiation of allergen immunotherapy within 3 months prior to Visit 1 or a plan to begin therapy or change its composition during the screening period or the randomized treatment period.
- E 15. Participant who has taken: anti-IgE therapy (eg, omalizumab) within 130 days (4 months) prior to Screening (Visit 1) or any other immune-directed biologic therapy (eg, anti-IL5, anti-IL5R, anti-TSLP, anti-IL6, anti-IL17, anti-IL23, anti-IL12/23, anti-IL4ra, etc) or systemic immunosuppressant (eg, methotrexate, any anti-TNF mAbs, B and/or T-cell targeted immunosuppressive therapies, JAK inhibitors) within 2 months or 5 half-lives prior to Screening (Visit 1), whichever is longer.
- E 16. Participants who have received live attenuated vaccine(s) within 4 weeks before Screening (Visit 1) or plans to receive such vaccines during the study are excluded.

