6.9.1 Rescue therapy

During the study treatment and follow-up periods, based on clinical evaluation, in case of worsening of signs and/or symptoms/acute sinusitis requiring medical intervention, the Investigator may consider rescue treatment with:

- Systemic antibiotics (up to 2 weeks) in case of acute infection.
- Short course SCS (prednisone or equivalent prednisolone up to 7 days; avoid use 4 weeks before Week 24 or Week 52, if possible).
- Sinonasal surgery for CRSwNP (8 weeks of IMP treatment is recommended prior to surgery to allow onset of treatment effect).

Participants receiving rescue treatment other than surgery during the study should continue on study drug unless the Investigator decides to withdraw the study treatment. Before starting treatment with SCS participants should come to the study site for the clinical assessments. It is recommended to avoid use of SCS as rescue therapy during the Week 20 to Week 24. If a participant must use SCS during this period to control worsening of symptoms based on Investigator judgment the site should make every effort to schedule the Week 24 CT scan prior to SCS rescue therapy. For participants who undergo or are planned for surgery for CRSwNP, the Investigator may decide to continue IMP up to the time of surgery or EOT, whichever date

comes first. At the time of surgery participants will be permanently discontinued from study intervention and assessed as soon as possible using the procedures normally planned for the EOT visit. In any case participants who prematurely discontinued the intervention will be encouraged to return to the study site for the efficacy and safety assessments planned at EOT visit and for additional visits. Additional appropriate medical/therapy per local guideline or per Investigators decision may be considered to use as rescue medicine.

The date and time of rescue medication administration as well as the name and dosage regimen of the rescue medication must be recorded in the eCRF.

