9.2 STATISTICAL ANALYSES

9.2.1 General considerations

The baseline value is defined as the last available value before the first dose of double-blind IMP. For participants randomized but not treated, the baseline value is defined as the last available value before randomization.

For endpoints defined using the data collected on the eDiary (such as NCS and TSS), baseline is defined as the average of the scores in the 7 days prior to randomization; for the baseline to EOT analysis, the average of the scores from the preceding 28 days to the corresponding timepoint will be defined as the analysis score for that timepoint.

Unless otherwise specified, analyses will be performed by intervention group (and overall for baseline and demographics characteristics).

The observation period will be divided into 4 segments:

- The **pre-treatment** period is defined as the period up to first IMP administration.
- The **TE period** is defined as the period from the first IMP administration to the last IMP administration + 154 days (ie, to the end of 20-week safety follow-up period).
The TE period includes the following 2 periods:
 - The **on-treatment period** defined as the period from the first IMP administration to the last administration of the IMP + 14 days.
 - The **residual treatment period** defined as the period from the end of the on-treatment period to the end of the TE period.
- The **post-treatment period** defined as the period from the end of the TE period.

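### Section 6.9 ends the live-attenuated vaccine ban at Week 52, two weeks after the last injection, leaving up to 140 days of residual treatment without an on-study rule

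*Protocol*

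**What the plan says.** **The conduct rule.** Section 6.9 opens its list of prohibited treatments with "The following concomitant treatments are not permitted during the screening period and the randomized treatment period". Live-attenuated vaccines are one item on that list and have no window of their own. Appendix 15 (section 10.15) names the vaccines but sets no dates.

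**The periods.** Section 4.1 lists three: screening, a 52-week randomized intervention period, and a 20-week post-treatment safety follow-up. Where a rule is meant to reach follow-up, the text can say so. Section 6.9.1 on rescue therapy begins "During the study treatment and follow-up periods, based on clinical evaluation".

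**The entry rule.** E 16 in section 5.2 concerns recent live vaccination and future plans: participants who had such a vaccine within 4 weeks before screening "or plans to receive such vaccines during the study are excluded".

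**The analysis periods.** Section 9.2.1 runs the treatment-emergent period to "last IMP administration + 154 days (ie, to the end of 20-week safety follow-up period"). Within it, the on-treatment period is "defined as the period from the first IMP administration to the last administration of the IMP + 14 days", and the residual treatment period is "defined as the period from the end of the on-treatment period to the end of the TE period".

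**Exposure.** Footnote k of the schedule of activities (section 1.3) places the last dose at Week 50. Section 4.3 expects mean steady-state troughs for the two regimens to exceed the 90% target-occupancy concentration and the 17 mg/L preclinical efficacy threshold, respectively.

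**The concern.** The ban lapses while the protocol itself still regards the participant as exposed. A site could give a listed live vaccine at Week 53, three weeks after the last injection, without a protocol deviation. An adverse event that followed would count as treatment-emergent.

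Other precautions do run on. Contraception under I 06 (section 5.1) continues for at least 20 weeks after the last dose. The ban on inhaled tobacco in section 5.3.2 lasts until after the final follow-up visit. Serum itepekimab is still sampled at Week 72. E 16 looks across the whole study, but only for vaccines already planned when the participant enters.

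What is at stake is participant safety in follow-up, and a cleaner reading of infections reported there. Section 2.3.1 names serious infections, including opportunistic ones, as important potential risks of itepekimab. Alpha, power and sample size are not affected.

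**Working it through.** **Inputs.** In the schedule of activities, Week *w* falls on Day 7*w* + 1, so Week 50 is Day 351, Week 52 (end of treatment) is Day 365 and Week 72 (end of study) is Day 505. Section 9.2.1 supplies the offsets of 14 and 154 days.

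**Reproducing the protocol's own figure.** For a participant dosed to Week 50:
- On-treatment period ends: 351 + 14 = Day 365, the Week 52 visit.
- Treatment-emergent period ends: 351 + 154 = Day 505, the Week 72 visit. This agrees with the statement in 9.2.1 that it closes with the 20-week follow-up.
- Residual treatment period: 154 − 14 = 140 days = 20 weeks.

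**Uncovered time.** Read the randomized treatment period as the 52 weeks of section 4.1, so that the ban ends on Day 365. For a last dose at Week *w*:

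uncovered days = max(0, (7*w* + 1 + 154) − 365) = max(0, 7*w* − 210)

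| Last dose | Treatment-emergent period ends | Uncovered days |
|---|---|---|
| Week 50 | Day 505 (Week 72) | 140 |
| Week 40 | Day 435 (Week 62) | 70 |
| Week 30 | Day 365 (Week 52) | 0 |
| Week 10 | Day 225 (Week 32) | 0 |

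For a participant dosed to Week 50, the whole residual treatment period lies outside the ban. For a last dose at or before Week 30, none of it does. Participants who enter LTS18420 leave this study at the end-of-treatment visit and have no follow-up here.

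**Exposure when the ban lapses.**
- Q2W arm: last active dose at Week 50, so Week 52 is one full dosing interval later, that is, at trough.
- Q4W arm: the protocol does not say whether active or placebo comes first. Active first gives Weeks 0, 4, …, 48 and 52 − 48 = 4 weeks, again at trough. Placebo first gives Weeks 2, 6, …, 50 and 52 − 50 = 2 weeks, mid-interval. Both orders give the 13 active doses of section 6.1.1.

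So in either arm the ban ends no later than a dosing trough, where section 4.3 expects the mean concentration to be above its activity threshold.

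**Choice of end point for a longer ban.** Copying the 20-week contraception minimum gives 351 + 140 = Day 491 (Week 70), 14 days short of the treatment-emergent period. Using 154 days gives Day 505 and matches 9.2.1 exactly.

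**The case against.** The best defence is that Week 52 is a deliberate, uniform end point for the whole 6.9 list. The residual treatment period is a device for classifying adverse events and does not govern concomitant therapy. Without a stated rationale or half-life, the defence runs, a Week 52 end cannot be called wrong.

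Part of this stands. The protocol never ties the vaccine ban to the infection risk: Table 1 lists the mitigations for serious infection and does not mention vaccines. How fast concentrations fall in follow-up cannot be read from the document. The safeguards are also real. E 16 removes foreseeable vaccinations at entry, section 6.9 requires every vaccine received during the study to be recorded, and section 8.4.1 collects adverse events to the end of study. However, recording a vaccine does not prevent it, and section 4.3 is enough to show that the ban lapses with drug expected to be active. Most other items on the list can confound efficacy, and the key endpoints are complete by Week 52; live vaccines are there for a different reason.

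A reader might go further in three ways that the text does not support:
- *E 16 contradicts 6.9.* It does not. E 16 is an entry screen and 6.9 a conduct rule, and both can be followed together.
- *All 210 participants go unprotected for 140 days.* That would need LTS18420 not to open and everyone to be dosed to Week 50.
- *The ban should run to end of study for everyone.* Someone whose last dose is at Week 10 leaves the treatment-emergent period at Week 32. Holding that person to Week 72 goes 40 weeks beyond the window on which the argument rests.

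**Conclusion.** The point holds as a modest, inexpensive safety improvement. The live-vaccine ban in 6.9 ends two weeks after the last scheduled injection, with active concentrations still expected and the residual treatment period just beginning, and no other rule covers an unplanned live vaccine after that. The uncovered time is up to 140 days for participants dosed to Week 50 who do not enter LTS18420, less for earlier last doses, and nil for a last dose at or before Week 30.

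These figures assume that the ban runs to Week 52 even for someone who has stopped IMP. If the randomized treatment period were taken to end when a participant stops dosing, early discontinuers would be uncovered as well, so the wording should settle this. The protocol gives no live-vaccination rate, half-life or reason for the ban, so neither an event count nor a harm rate can be inferred.

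**What to change.** In section 6.9, take live-attenuated vaccines out of the common list and give them their own sentence:

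*Live-attenuated vaccines (Appendix 15) are not permitted from screening to the end of the randomized treatment period (Week 52) or 154 days after the last IMP dose, whichever is later; participants entering LTS18420 follow that protocol.*

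A participant dosed to Week 50 is then covered to Day 505. One whose last dose is at Week 10 stays covered to Week 52 and no longer. E 16 and the rest of the 6.9 list can stay as they are.

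The cost is one moved list item and one sentence, in an amendment that needs IRB/IEC approval before use (section 10.1.1). No visits, tests or analyses are added. Because the trial is blinded, some participants in follow-up, including those on placebo, would defer a live vaccine by up to 20 weeks beyond the present Week 52 limit.
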